**SCHEMA**

Disease: Patients with Intermediate Risk Prostate Cancer:	Treatment: 6 months of enzalutamide. EBRT*** beginning 7-10 weeks after initiating enzalutamide. 7560-7920 cGy in 180cGy fractions	Endpoints: Primary-PSA level at completion of therapy compared to historical controls with LH-RH agonists Secondary: 1) Quality of Life 2) Hormonal levels 3) Body fat measurements
---	--	--

**Timeline**

\* Fiducial placement and biopsy 3-7 weeks after initiating enzalutamide    \*\*

Radiation initiated 7-10 weeks after initiating enzalutamide.

\*\*\* Patients that are unable to complete enzalutamide therapy will still be treated with EBRT per SOC

\*\*\*\* 28 day cycle allows for +/- 3 day window

## 1. OBJECTIVES

### 1.1 Study Design

The goal of this exploratory study is to assess efficacy of adding enzalutamide in the neoadjuvant and adjuvant setting in combination with external beam radiation therapy (EBRT). The population will be prostate cancer patients with intermediate risk prostate cancer, choosing radiation therapy as their primary form of therapy. This is a phase II single arm trial that has as its primary objective to estimate the proportion of patients with PSA  $\leq 0.2$  ng/ml at the completion of therapy. This endpoint has been shown to be predictive of long term response in a similar risk-group of patients treated with radiation therapy and LHRH agonists. Secondary endpoints include measurement of serum hormone levels, health-related quality of life (HRQoL) and body fat measurements. It is expected that enzalutamide therapy in contrast to LHRH agonists has a much better profile for these secondary outcomes. Correlative studies will center on understanding enzalutamide's mechanism of action. Data from this trial, if convincing, would lead to a Phase III randomized trial comparing LHRH agonists to enzalutamide as neoadjuvant and adjuvant therapy in combination with EBRT.

On this study patients will be treated with 6 months of Xtandi (enzalutamide). Approximately one-third of the way through this treatment they will receive EBRT. Starting on Day 1, all patients will ingest enzalutamide **160 mg/day** at the same time each day without breaks (except as outlined for toxicity), with or without food, for 6 (28 day +/-3 days) cycles. Dose reduction of enzalutamide to 120 mg/day is allowed with the approval of the Medical Monitor, [name] (Section 6.2.2.3). Patients will be instructed to return all unused capsules at each study visit to assess compliance and will receive study drug every 28 days (+/-3 days) for 6 cycles (24 weeks).

### 1.2 Primary Objectives

1. Estimate the proportion of patients whose PSA level at the end of six (28 day +/-3 days) cycles of enzalutamide and EBRT is  $\leq 0.2$  ng/ml.

### 1.3 Secondary Objectives

1. Assessment of the effect of treatment on health-related quality of life including fatigue, sleep quality, as well as urinary, bowel, sexual and hormonal functioning.
2. Assessment of the effect of treatment on serum sex hormones including androgens and estrogens.
3. Assessment of the effect of treatment on body fat distribution and muscle mass.
4. Assessment of safety and tolerability according to adverse event reporting during the trial.
5. Assessment of the effect of treatment on bone metabolism.

CONFIDENTIAL

This document is confidential. Do not disclose or use except as authorized.

## 1.4 Correlative Objective

1. Assessment of cellular location of androgen receptor expression using immunohistochemistry on prostate tissue samples obtained during fiducial placement.

## 2. BACKGROUND

### 2.1 Enzalutamide

Please refer to the Investigator's Brochure for further information on the pharmacology of enzalutamide.

Enzalutamide (enzalutamide) is a potent androgen receptor signaling inhibitor that blocks several steps in the androgen receptor signaling pathway. Enzalutamide competitively binds to the androgen receptor with an  $IC_{50}$  of 36 nM, compared to 160 nM for bicalutamide (an androgen receptor antagonist commonly used for ADT [2, 3]). In addition, enzalutamide inhibits nuclear translocation of activated receptors and inhibits the association of the activated androgen receptor with DNA, even in the setting of androgen receptor overexpression and in prostate cancer cells resistant to anti-androgens. Enzalutamide treatment decreases the growth of prostate cancer cells and can induce cancer cell death and tumor regression. Effective inhibition of androgen receptor signaling by enzalutamide (observed *in vitro*) blocks the oncogenic effects of androgen metabolism by tumor cells and the up regulation of the androgen receptor. In addition, enzalutamide induces immediate prostate cancer apoptosis, an effect not seen with antiandrogens (e.g., bicalutamide) (3) Furthermore, enzalutamide has no known agonist activity when the androgen receptor is overexpressed.

Enzalutamide treatment in a prostate cancer xenograft model resulted in a dose-dependent reduction in tumor volume: 1/7 tumors in the low-dose group (1 mg/kg/day) and 3/7 tumors in the high-dose group (50 mg/kg/day) became unmeasurable. In contrast, bicalutamide had little effect on tumor growth.

Enzalutamide was non-mutagenic/clastogenic in *in vitro* genotoxicity assays (reverse mutation and mouse lymphoma). Repeat-dose oral toxicology studies were conducted with durations of up to 6 months in rats and 3 months in dogs. The most prominent effects of enzalutamide in these species were reductions in prostate, epididymis, and/or seminal vesicle weight, all of which are consistent with the expected antiandrogen pharmacology of enzalutamide. These decreases were accompanied by corresponding histopathological findings of prostatic and seminal vesicle secretory depletion and/or atrophy, with epididymal atrophy in dogs only. Hypospermatogenesis and degeneration of seminiferous tubules in testes have been observed in dogs, but not in rats. The enzalutamide-related male sex organ findings reversed, or tended to reverse, after at least 8 weeks of recovery. Reversible hepatocellular hypertrophy, associated with liver weight increases, was a consistent finding of enzalutamide in rats, but not in dogs. Several additional histopathological findings (mostly in endocrine tissues) definitively related to enzalutamide treatment in the 26-week study in rats included hypertrophy/hyperplasia in adrenals, pituitary, and thyroid; atrophy in male mammary gland; gland/lumen dilatation and lobular hyperplasia in

CONFIDENTIAL

This document is confidential. Do not disclose or use except as authorized.

Version 13.0 Protocol Version Date: 1/09/2015

female mammary gland; and luminal dilatation in the uterus. In a short-term reversibility study in male dogs, enzalutamide treatment did not result in detectable permanent effects to male reproductive organs.

Cardiovascular safety was evaluated in vitro in patch-clamped mammalian cells expressing the hERG channel. The results showed that enzalutamide inhibited the hERG current with an IC50 of 16.2  $\mu$ M (7.29  $\mu$ g/mL). The highest free concentration of enzalutamide expected in patient plasma at a steady-state dose of 160 mg/day is well below the hERG IC50 value. The major active metabolite of enzalutamide (M2) was also shown to weakly inhibit the hERG channel with an IC50 of 18.6  $\mu$ M (8.38  $\mu$ g/mL).

In mice, rats, and dogs, orally administered enzalutamide had a half-life (t1/2) of approximately 0.25 to 3 days. The t1/2 did not appear to be affected by the dose size; however, bioavailability appeared to decrease with increasing dose size. Plasma protein binding of enzalutamide in human plasma ranged from 97% to 98% and was similar in mice, rats, rabbits, and dogs.

Co-administration of a strong CYP2C8 inhibitor (gemfibrozil) increased the composite area under the plasma concentration-time curve (AUC) of enzalutamide plus N-desmethyl enzalutamide in healthy volunteers. Co-administration of enzalutamide with strong CYP2C8 inhibitors should be avoided (see APPENDIX F).

The effects of CYP2C8 inducers on the pharmacokinetics of enzalutamide have not been evaluated in vivo. Co-administration of enzalutamide with strong CYP2C8 inducers (e.g., rifampin) may alter the plasma exposure of enzalutamide and should be avoided (see APPENDIX F).

The effects of CYP3A4 inducers on the pharmacokinetics of enzalutamide have not been evaluated in vivo. Co-administration of enzalutamide with strong CYP3A4 inducers (e.g., carbamazepine, phenobarbital, phenytoin, rifabutin, rifampin, rifapentine) may decrease the plasma exposure of enzalutamide and should be avoided. (see APPENDIX F) Moderate CYP3A4 inducers (e.g., bosentan, efavirenz, etravirine, modafinil, nafcillin) and St. John's Wort may also reduce the plasma exposure of enzalutamide and should be avoided.

Enzalutamide is a strong CYP3A4 inducer and a moderate CYP2C9 and CYP2C19 inducer in humans. At steady state, enzalutamide reduced the plasma exposure to midazolam (CYP3A4 substrate), warfarin (CYP2C9 substrate), and omeprazole (CYP2C19 substrate).

Concomitant use of enzalutamide with narrow therapeutic index drugs that are metabolized by CYP3A4 (e.g., alfentanil, cyclosporine, dihydroergotamine, ergotamine, fentanyl, pimozide, quinidine, sirolimus and tacrolimus), CYP2C9 (e.g., phenytoin, warfarin), pentobarbital, ketoconazole, sertaraline, digitoxin, haloperidol, ketamine, doxycycline, isoniazid, ciprofloxacin and CYP2C19 (e.g., S-mephenytoin) should be avoided if possible, as enzalutamide may

CONFIDENTIAL

This document is confidential. Do not disclose or use except as authorized.

Version 13.0 Protocol Version Date: 1/09/2015

decrease their exposure. If co-administration with warfarin cannot be avoided, conduct additional INR monitoring

Additional nonclinical information can be found in the Investigator's Brochure.

### **2.1.1 Previous Human Experience**

The tolerability, pharmacokinetics (PK), and antitumor activity of enzalutamide were studied in a multicenter, open-label, dose-escalation study of enzalutamide in 140 patients with advanced prostate cancer. Patients were treated with enzalutamide at doses of 30 to 600 mg/day until disease progression or intolerable side effects developed.

In this study, enzalutamide was absorbed rapidly after oral administration, with the median time to maximum plasma concentration ( $C_{max}$ ) after a single dose occurring at 1.00 hour (range 0.42 to 4.00 hours postdose). The PK of enzalutamide was essentially linear with no major deviations from dose proportionality in  $C_{max}$  or area under the curve values in the dose range of 30 to 600 mg. The terminal  $t_{1/2}$  for enzalutamide after a single dose was approximately 6 days (range 3 to 10 days) and did not appear to be affected by the dose size. In accordance with the long  $t_{1/2}$ , it took approximately 1 month after the start of a daily dose regimen to reach steady state. On achievement of steady state, the mean trough concentrations ( $C_{min}$ ) in individual patients remained constant for several months, suggesting time-linear PK. With daily oral administration of 150 mg/day, the mean accumulation index for enzalutamide was approximately 11, reflecting the long  $t_{1/2}$  relative to the dosing interval. Due to its slow clearance from plasma, the daily fluctuation in steady-state enzalutamide concentrations was low. The mean peak-to-trough ratios ( $C_{max}/C_{min}$ ) was 1.2 (range 1.14 to 1.3), indicating that variability in steady-state  $C_{max}$ ,  $C_{min}$ , and area under the curve values was low ( $\leq 30\% CV$ ). At 160 mg/day, the mean steady-state  $C_{min}$  is expected to be approximately  $12 \pm 4 \mu\text{g/mL}$ . Full PK profiles were linear and consistent over the dose range studied.

Fatigue was the most frequently reported adverse event, with dose-dependent increases of Grade 3 fatigue (0% at 150 mg/day, 9% at 240 mg/day, 15% at 360 mg/day, and 20% at 480 mg/day). The dose of 240 mg/day was defined as the maximum tolerated dose. At doses of 240 mg and above, an increasing proportion of patients needed dose reductions for fatigue. Dose reductions were needed in 1 of 29 patients (3%) that received 240 mg/day, 3 of 28 patients (11%) that received 360 mg/day, and 5 of 22 patients (23%) that received 480 mg/day, and 0 of 58 patients that received 30, 60, or 150 mg/day. After dose reductions, the symptoms resolved. Only 1 patient discontinued treatment due to fatigue with an onset coinciding with prostate specific antigen (PSA) rise. Overall, the most common mild (grade 2) adverse events were fatigue ( $n = 38$  [27.1%]), nausea ( $n = 12$  [8.6%]), dyspnea ( $n = 11$  [7.9%]), anorexia ( $n = 8$  [5.7%]), and back pain ( $n = 8$  [5.7%]). Fatigue, nausea, and anorexia were the only mild adverse events with an increasing incidence as the dose of enzalutamide was increased. None of the grade 2 events required dose modification or the discontinuation of treatment, apart from 1 patient treated at 480 mg/day who had nausea at baseline and stopped therapy after 7 weeks.

CONFIDENTIAL

This document is confidential. Do not disclose or use except as authorized.

Version 13.0 Protocol Version Date: 1/09/2015

In the randomized clinical trial, 7 of 800 (0.9%) patients treated with enzalutamide 160 mg once daily experienced a seizure. No seizures occurred in patients treated with placebo. Seizures occurred from 31 to 603 days after initiation of enzalutamide. Patients experiencing seizure were permanently discontinued from therapy and all seizures resolved. There is no clinical trial experience re-administering enzalutamide to patients who experienced seizures.

The safety of enzalutamide in patients with predisposing factors for seizure is not known because these patients were excluded from the trial. These exclusion criteria included a history of seizure, underlying brain injury with loss of consciousness, transient ischemic attack within the past 12 months, cerebral vascular accident, brain metastases, brain arteriovenous malformation or the use of concomitant medications that may lower the seizure threshold.

The antitumor activity of enzalutamide was assessed by post-therapy changes in PSA, soft tissue and osseous disease, and circulating tumor cell count. Prostate specific antigen declines of  $\geq$  50% from baseline were observed in 62% of patients. Radiographic evidence of disease control (i.e., no progression) was also observed in the majority of patients (3).

Based on these results, 2 placebo-controlled, randomized Phase 3 studies (AFFIRM and PREVAIL) were initiated to evaluate the efficacy and safety of enzalutamide in patients with advanced prostate cancer. The AFFIRM study evaluated the safety and efficacy of enzalutamide in 1199 patients who progressed on docetaxel (4). This study showed a survival benefit in favor of enzalutamide (hazard ratio 0.631 p < 0.0001, median overall survival of 18.4 versus 13.6 months for enzalutamide and placebo, respectively (4). The PREVAIL study was designed to evaluate the safety and efficacy of enzalutamide in patients who have not yet received chemotherapy for their metastatic disease; this study is ongoing. The AFFIRM study, however, lead to the approval of this drug for the indication for CRPC with metastatic disease following docetaxel in September 2012.

## 2.2 Study Disease

Prostate cancer is the most commonly diagnosed non-cutaneous cancer diagnosed in the US male population and the second leading cause of cancer death. In 2008, 214 633 new cases were diagnosed and 28,411 men died of prostate cancer. Standard options for men with early stage prostate cancer can include active surveillance, prostatectomy, external beam or brachytherapy radiation and hormonal therapy. Treatment recommendation depends on extent of local disease and other issues such as age of the patient, pre-existing medical condition. Often patients have several management options. Including in this decision making process are the risks and toxicities associated with each treatment approach. Both retrospective reports and prospective trials have shown the usefulness of categorizing patients with prostate cancer using multimodality staging. By combining the presenting tumor stage (AJCC- T stage), the finding on rectal exam and the pre-treatment serum PSA level, patients fall into a low, intermediate or risk category.

CONFIDENTIAL

This document is confidential. Do not disclose or use except as authorized.

Version 13.0 Protocol Version Date: 1/09/2015

Definitive treatment is generally recommended for men with a good life expectancy without potentially life shortening co-morbidities with Intermediate Risk prostate cancer. The addition of hormonal treatments (therapies that reduce testosterone) has been shown to be efficacious to external beam in several prospective randomized trials. The reason for this beneficial effect is not understood. One explanation for this effect is the cytoreductive effects of hormonal therapy which increases the probability of local tumor control with external beam radiotherapy. These trials were initiated in the era when the total dose external beam dose was low by contemporary standards. In fact, the RTOG is revisiting the role for androgen ablation with high dose radiotherapy in the intermediate risk prostate cancer patient (RTOG 0815).

A barrier to treatment with androgen ablation with external radiotherapy are the toxicities associated with low serum testosterone levels. These include loss of libido, erectile dysfunction, hot flashes and weight gain. Since serum testosterone levels are not affected by the androgen receptor blockade of bicalutamide, hot flashes, loss of libido and sexual side effects are less common. As stated above, these are nearly universal side effects of LH-RH agonist therapies that low serum testosterone to castrate levels. However bicalutamide is a partial agonist of the androgen receptor and there is concern regarding its efficacy as monotherapy, particularly at the 50 mg per day dose (the currently approved dose). D'Amico et al has shown that PSA nadir after external beam and 6 months of LH-RH agonist therapy with bicalutamide is predictive of disease free survival and metastasis free survival (1). If the PSA nadir is 0.2 ng/ml or lower, there is improvement in outcome. Potentially with longer follow-up in this study, there will be improved survival if these low PSA levels can be achieved. Therefore, PSA nadir at the end of external beam and 6 months of hormonal therapy is a surrogate endpoint for disease free survival and metastasis free survival.

### **2.3 Rationale**

Presently most patients with intermediate risk prostate cancer receive neoadjuvant, concurrent and adjuvant hormonal therapy with external beam irradiation. Multiple studies have shown that the addition of HT improves survival to external beam radiation (5,6) However androgen deprivation induced by LH-RH agonists consistently results in hot flashes, loss of libido, loss of sexual functioning, weight gain, changes in metabolism, loss of muscle mass and fatigue (7, 8).

In contrast, treatment with the anti-androgens bicalutamide or flutamide has minimal side effects, likely related to the fact that these agents do not suppress serum testosterone. Enzalutamide has the potential to have similar anti-tumor effects as LH-RH agonist without the toxicity associated with castrate testosterone levels. If it were shown that enzalutamide (enzalutamide) could be used as an effective adjuvant treatment for prostate cancer without androgen deprivation it would have dramatic and significant impact, including expanding its use to those patients who may have more intermediate risk and/or are unable to tolerate the toxicities associated with androgen deprivation

We have chosen as the primary endpoint the assessment of the proportion of patients whose PSA level is  $\leq 0.2$  ng/ml at the conclusion of therapy. This endpoint was chosen because patients that

CONFIDENTIAL

This document is confidential. Do not disclose or use except as authorized.

Version 13.0 Protocol Version Date: 1/09/2015

achieve this value after treatment with LHRH analogs in combination with EBRT have an excellent prognosis compared to patients that demonstrate higher PSA levels (1, 9). Furthermore, demonstration of PSA levels of  $\leq 0.2\text{ng/ml}$  in a significant number of patients treated on this study would be strong motivation to perform a phase III randomized trial comparing enzalutamide to LHRH analog therapy in the same setting.

#### **2.4 Correlative Studies Background**

Patients on this trial will, of necessity, have placement of fiducials that are used to guide the radiation treatment. These are placed in the outpatient setting and require exactly the same efforts as does a prostate biopsy (pre-treatment antibiotic therapy, ultrasound guidance, patient positioning etc.). Fiducials are routinely placed 3-7 weeks after initiating enzalutamide. At this juncture patients that consent will undergo two additional core samples to be obtained from the prostate, likely in the position of previous disease as documented in the core biopsy diagnostic report. The aim of obtaining these samples will be for analysis of localization of the androgen receptor by immunohistochemistry. As discussed, data suggest that one of the mechanisms behind enzalutamide's' effectiveness is to trap the AR in the cytoplasm and block its access to the nucleus where it can act as a transcription factor.(3). The pattern of expression from these samples can be compared to the pattern of AR localization in the patient's pre-treatment core biopsies and from patient samples available to us from our tumor bank. The latter patients have been treated with or without LHRH analogs, both of which would be important controls.

CONFIDENTIAL

This document is confidential. Do not disclose or use except as authorized.

### **3. PARTICIPANT SELECTION**

Participants must meet the following criteria on screening examination to be eligible to participate in the study:

#### **3.1 Inclusion Criteria**

Study population: Participants must have histologically confirmed malignancy and are candidates for external beam radiation therapy. Patients eligible for this study must have intermediate risk disease defined as PSA values between 10-20 ng/ml and/or T2b-c and/or Gleason grade 7. If all three are present, less than 50% of the core biopsies can be positive.

Patients previously diagnosed with low risk (Gleason score < 6, clinical stage < T2a, and PSA< 10) prostate cancer undergoing active surveillance who are re-biopsied and found to have intermediate risk disease according to the protocol criteria are eligible for enrollment within 180 days of the repeat biopsy procedure.

**3.1.1** Age 18 years or more.

**3.1.2** Life expectancy of greater than 1 year.

**3.1.3** ECOG performance status  $\leq 2$  (see Appendix D).

**3.1.4** Participants must have normal organ and marrow function as defined below:

- Leukocytes  $\geq 3,000/\text{mcL}$
- Platelets  $\geq 80,000/\text{mcL}$
- Total bilirubin  $< 2X$  institutional upper limit
- AST (SGOT)/ALT (SGPT)  $\leq 2.5 X$  institutional upper limit of normal
- Creatinine  $< 2x$  institutional limits .

**3.1.5** The effects of enzalutamide on the developing human fetus are unknown. For this reason and because enzalutamide may be teratogenic, men must agree to use adequate contraception (hormonal or barrier method of birth control; abstinence) prior to study entry and for the duration of study participation.

**3.1.6** Ability to understand and the willingness to sign a written informed consent document.

CONFIDENTIAL

This document is confidential. Do not disclose or use except as authorized.

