### 3.2 Exclusion Criteria

Patients must NOT meet any of the following exclusion criteria

- 3.2.1 Received an investigational agent within 4 weeks prior to enrollment (see section 5.3.12).
- 3.2.2 Stage T4 prostate cancer by clinical examination or radiologic evaluation.
- 3.2.3 Hypogonadism or severe androgen deficiency as defined by screening serum testosterone less than 50 ng/dL below the normal range for the institution.
- 3.2.4 Prior androgen deprivation, chemotherapy, surgery, or radiation for prostate cancer.
- 3.2.5 Receiving concurrent androgens, anti-androgens, estrogens, or progestational agents, or received any of these agents within the 6 months prior to enrollment or having taken finasteride or dutasteride within 30 days of registration.
- 3.2.6 History of another active malignancy within the previous 5 years other than curatively treated nonmelanomatous skin cancer and superficial bladder cancer. Participants treated for malignancy with no relapse within two years are eligible to participate in the study.
- 3.2.7 Uncontrolled intercurrent illness including, but not limited to, ongoing or active infection.
- 3.2.8 Severe concurrent disease, infection, or co-morbidity that, in the judgment of the Investigator, would make the patient inappropriate for enrollment.
- 3.2.9 Unwilling to use contraceptives while on study if relevant to patient.
- 3.2.10 History of seizure or any condition or concurrent medication that may predispose to seizure.
- 3.2.11 History of loss of consciousness or transient ischemic attack within 12 months prior to enrollment.
- 3.2.12 Clinically significant cardiovascular disease, including:
  - Myocardial infarction within 3 months of enrollment;
  - Uncontrolled angina within 3 months of enrollment;
  - Congestive heart failure New York Heart Association (NYHA) class 3 or 4, or history of congestive heart failure NYHA class 3 or 4 in the past, unless a screening echocardiogram or multi-gated acquisition scan performed within 3 months results in a left ventricular ejection fraction  $\geq 45\%$ ;
  - History of clinically significant ventricular arrhythmias (e.g., ventricular tachycardia, ventricular fibrillation, torsades de pointes);
  - History of Mobitz II second degree or third degree heart block without a permanent pacemaker in place;
  - Hypotension as indicated by systolic blood pressure  $< 86$  mmHg on 2 consecutive measurements at the Screening visit;

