# **13. STATISTICAL CONSIDERATIONS**

## **13.1 Sample Size/Accrual Rate**

The primary objective is to estimate the proportion of patients having intermediate risk CaP treated with external beam radiation therapy (EBRT) and enzalutamide whose PSA level at the end of six cycles of enzalutamide and EBRT is  $\leq 0.2$  ng/ml. In a single stage design, seventy-one patients will be enrolled. Assuming 10% ineligibility, the target evaluable sample size is 64 patients. The null hypothesis is 60% of patients achieving PSA nadir  $\leq 0.2$  ng/ml. The historical rate will serve as the alternative in this design. Based on research by D'Amico et al, the proportion of patients achieving PSA level  $\leq 0.20$  ng/ml at the end of EBRT and 6 months of leuprolide acetate neo-adjuvant/adjuvant treatment is 75%. With a sample size of 64 evaluable patients, if the number achieving PSA level  $\leq 0.2$  ng/ml is 44 or more, then the hypothesis that the percentage achieving PSA level  $\leq 0.2$  ng/ml is  $\leq 60\%$  is rejected with a target error rate of  $\alpha=0.10$  (actual error 0.095), whereas if the number is 43 or less, then the hypothesis that the percentage achieving PSA level  $\leq 0.2$  ng/ml is  $\geq 75\%$  is rejected with a target error rate of  $\beta=0.10$  (actual  $\beta=0.099$ ). We also will report exact binomial 90% confidence intervals on the observed proportion. Patients that discontinue early or are missing the end of treatment (cycle 6) PSA will be considered failures. Sensitivity analysis on the primary endpoint that includes counting a patient as a success if there is record of PSA level  $\leq 0.20$  ng/ml ever on treatment will be performed. We expect to accrue 2-3 patients per month at the three DF/HCC hospitals, BWH and DFCI and therefore accrual duration is expected to be 24-36 months.

CONFIDENTIAL

This document is confidential. Do not disclose or use except as authorized.

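### Section 3.1 accepts any one intermediate-risk feature with no ceiling on the others and 3.2.2 bars only T4, so as written some men above the stated intermediate-risk population are eligible

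*Combined protocol and SAP*

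**What the plan says.** Section 1.1 sets the population: "The population will be prostate cancer patients with intermediate risk prostate cancer, choosing radiation therapy as their primary form of therapy". The Schema and Section 13.1 also describe the patients as intermediate risk.

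Section 3.1 turns this into a rule. The required disease is "intermediate risk disease defined as PSA values between 10-20 ng/ml and/or T2b-c and/or Gleason grade 7". One further limit follows: "If all three are present, less than 50% of the core biopsies can be positive". Men coming from active surveillance must be "found to have intermediate risk disease according to the protocol criteria are eligible for enrollment within 180 days of the repeat biopsy procedure", which points back to the same list and adds no ceiling.

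Among the exclusions in Section 3.2, the only one on tumour extent is 3.2.2: "Stage T4 prostate cancer by clinical examination or radiologic evaluation". No criterion names Gleason 8-10, PSA above 20 or T3. Section 2.2 says that patients are sorted into risk categories "By combining the presenting tumor stage (AJCC- T stage), the finding on rectal exam and the pre-treatment serum PSA level", but gives no cut-offs.

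Section 13.1 tests the proportion with PSA at or below 0.2 ng/ml against a null of 60%, with a historical 75% as the alternative. It states that "the target evaluable sample size is 64 patients" and declares success at 44 or more.

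**The concern.** The and/or list is a floor without a ceiling. It asks whether a man has at least one intermediate feature. It does not ask whether another feature puts him above that range. A man can therefore satisfy the definition through one feature while another lies outside every range the protocol lists.

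The positive-cores limit adds an anomaly. It applies only when all three intermediate features are present, so raising one feature above its range switches the limit off. The rule is then stricter on the man with less adverse disease.

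There is no concurrent control, so who is enrolled bears directly on the observed proportion. A shortfall against 44 of 64 could reflect the drug or the mix of men treated. Section 13 plans no analysis of the primary endpoint by risk group to separate the two. According to Section 1.1, the result would inform a decision on a randomised phase III trial.

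**Working it through.** **1. Apply the written criteria to example men** (tumour criteria only, Sections 3.1 and 3.2).

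| Man | Listed feature met | Cores limit triggered? | T4? | As written |
|---|---|---|---|---|
| PSA 12, T2a, Gleason 9 | PSA | No | No | Eligible |
| PSA 35, Gleason 7, below T4 | Gleason | No | No | Eligible |
| T3, Gleason 7 | Gleason | No | No | Eligible |
| PSA 15, T2b, Gleason 7, 60% of cores positive | All three | Yes | No | Not eligible |
| PSA 15, T2b, Gleason 9, 60% of cores positive | PSA and stage | No | No | Eligible |
| PSA 5, T1c, Gleason 8 | None | No | No | Not eligible |

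The first three rows show the gap. Rows four and five differ only in Gleason score, and the man with the higher score is the one admitted. The last row marks the limit of the point: a man with a feature above the ranges qualifies only if he also has a listed feature.

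**2. Reproduce the design in Section 13.1.** Inputs: n = 64, success at 44 or more, null 0.60, alternative 0.75. With exact binomial tails:

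- P(X ≥ 44 | 64, 0.60) = 0.0953. The plan states an actual error of 0.095.
- P(X ≥ 44 | 64, 0.75) = 0.9007, so beta = 0.0993. The plan states 0.099.

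The plan's figures are right, and the eligibility wording does not enter them.

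**3. Illustrate the effect on power.** Assumption, not in the documents: a share h of the 64 men have a feature above the ranges and succeed at rate q, while the rest succeed at 75%. The overall rate is p = 0.75(1 − h) + q·h. For h = 10% and q = 40%, p = 0.675 + 0.040 = 0.715. P(X ≥ 44 | 64, p) is then:

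| Share h | q = 40% | q = 50% | q = 70% |
|---|---|---|---|
| 5% | 0.831 | 0.853 | 0.892 |
| 10% | 0.738 | 0.794 | 0.883 |
| 20% | 0.509 | 0.644 | 0.864 |

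The reference value with no such men is 0.901.

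**4. Illustrate the effect on the false-positive rate.** Suppose the remaining men are at the null rate: p = 0.60(1 − h) + q·h. With h = 10%, q = 40% and 50% give p = 0.58 and 0.59, and the chance of 44 or more is 0.05 and 0.07. With h = 20%, p = 0.56 and 0.58, and the chance is 0.03 and 0.05. All are below 0.095. If the added men do worse than the rest, the error is towards missing an effect.

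**The case against.** **A cap was plainly intended.** Section 2.2 describes categories into which patients fall, which reads as exclusive classes. Section 3.1 says that patients must have intermediate-risk disease. The target volume in 5.2.3.5 includes only the proximal 1.0 cm of seminal vesicle, and nodal fields are not permitted. Registration uses a checklist validated centrally (Section 4.2), which is not in the documents and may contain the cap. This stands as evidence of intent, and it means that actual enrolment of such men is unproven. It does not close the gap, because the sentence that uses the term also defines it, by the and/or list. The next paragraph of 3.1 describes low risk with a bound on all three features joined by *and*, so a bounded definition was within reach.

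**The benchmark may include such men.** A reader might infer that the 60% and 75% rates were set for a similar risk group, so that admitting higher-risk men must break the comparison. The documents do not say this. Section 1.1 refers to a similar risk group only when describing how well the endpoint predicts long-term response. Section 13.1 gives the 75% without a risk mix or a reference number. The title of reference 1 covers localised and locally advanced disease. If that is the source of the 75%, the historical series may itself contain higher-risk men. The objection stands: the size, and even the direction, of any mismatch is unknown.

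**The T4 line proves little.** A reader might infer from a T4-only exclusion that T3 was meant to be admitted. That is weak evidence. The protocol repeats itself elsewhere (contraception in 3.1.5 and 3.2.9, for example), so a redundant line is not out of character. What remains is that 3.1 and 3.2.2 draw different limits on stage and should be reconciled.

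**Conclusion.** The point holds as an error in a stated rule. As written, 3.1 and 3.2.2 together admit men whom the Schema and Sections 1.1 and 13.1 describe the trial as not being for, and the cores limit works the wrong way round for some of them.

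The consequence is possible confounding by case mix and possible loss of power. With 10% such men at an assumed 40-70% success, power is 0.74-0.88 instead of 0.90. Both the share and the success rates are assumptions, so these figures show sensitivity and are not an estimate.

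A reader might go further and call the result uninterpretable. The documents do not support that. If the added men do worse, the false-positive rate falls to about 0.03-0.07 from 0.095 under the assumptions in step 4, so a positive result would stand. The difficulty would lie in reading a negative one.

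**What to change.** Reword 3.1 so that eligibility requires at least one listed feature **and** no feature above the listed ranges: no PSA above 20 ng/ml, no Gleason above 7, no stage above T2c. Reconcile 3.2.2 with that limit.

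If the sponsor does intend to admit men above these ranges, change the stated population in the Schema and Sections 1.1 and 13.1 to say so, and report the primary endpoint by risk group.

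This is version 13.0, and Section 9.2.1 refers to tests collected under previous amendments, so men have apparently already been treated. For them, report the number with a feature above the listed ranges and add a sensitivity analysis of the primary endpoint without them.

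The cost is slightly fewer eligible men and an amendment needing IRB approval (Section 12.1). The sample size, the 44-of-64 rule and its stated error rates do not change. The rewording does not show that the 75% benchmark came from a matching population; it only makes clear whom the trial's own result describes.
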